# 2. Glossary

AE AR BHT BSFS BTXA CI	Adverse Event Adverse Reaction Barts Health NHS Trust Bristol Stool Form Scale Botulinum Toxin type A Chief investigator
CCCS	Chief investigator Cleveland Clinic constipation score
CRF	Case Report Form
CTIMP	Clinical Trial of an Investigational Medicinal Product
DD	Dyssynergic defaecation
EMG	Electromyography
FI	Faecal Incontinence
GP	General Practitioner
IBS	Irritable bowel syndrome
IBS-C	Irritable bowel syndrome with predominant constipation
ICF	Informed Consent Form
MDT	Multidisciplinary Team
NBRC	National Bowel Research Centre
NICE	The National Institute for Clinical Excellence
PI	Principal Investigator
PIS	Participant Information Sheet
REC	Research Ethics Committee
REDCap	Research Electronic Data Capture
SAE	Serious Adverse Event
SAR	Serious Adverse Reaction
SMG	Study Management Group
SMIS	St. Mark's incontinence score
USS	Ultrasound scan

# 4. Summary and synopsis

Short title	Infracoccygeal Botox for Dyssynergia
Methodology	Prospective observational study
Research Site	Royal London Hospital – Barts Health NHS Trust
Objectives / aims	
 
Primary objective:
 
To demonstrate technical feasibility of percutaneous infracoccygeal Botulinum toxin type A (BTXA) injection as an alternative to transanal injection to puborectalis muscle for the treatment of dyssynergic defaecation.
 
Secondary objectives: 
 
To assess safety of this technique
 
To assess patient acceptability of this technique
 
To derive pilot clinical efficacy data to inform future trials
 
 
 

Number of	10
participants	
Inclusion and	Inclusion criteria:
exclusion criteria	- Adult patients (age 18 - 80)
	
 
Diagnosis of dyssynergic defaecation by published criteria
 

	- Ability to understand written and spoken English
	- Ability and willingness to give informed consent
	Exclusion criteria:
	- Paediatric patients (age under 18)
	- Contraindications to BTXA, including pregnancy
	- Contraindications to infracoccygeal injection
	- Morbid obesity (BMI $\geq$ 40)
Statistical	Not applicable (descriptive summary statistics only)
methodology and	
analysis (if	
applicable)	
Study duration	12 months

### 5. Introduction

#### 5.1 Background

Patients with dyssynergic defaecation represent a subgroup of a larger group of patients presenting with symptoms of chronic constipation. The disorder is characterised by impaired stool expulsion as a result of inappropriate contraction of the pelvic floor musculation despite normal propulsive force during attempted defaecation. Failure of the puborectalis and/or anal sphincter muscles to relax during evacuation leads to a closed anal canal which prevents the emptying of stools. 

A Cochrane review in 2014 on the treatment of chronic constipation in adults demonstrated a high prevalence of dyssynergic defaecation and a variety of treatments. In this group, biofeedback was found to be superior to oral diazepam, sham treatment, and laxatives; while surgical procedures such as partial division of the puborectalis muscle were more efficacious, the risks of adverse reaction, namely incontinence, were high. Thus, biofeedback therapy is the current gold-standard for the treatment of dyssynergia. The success rate of biofeedback in correcting or improving the symptoms in patients with dyssynergia varies between 33% and 80%. Difficulty arises in those in whom biofeedback is unsuccessful, as there is little, and conflicting, low quality evidence on alternative therapies.

One further therapeutic option uses injection of Botulinum toxin type A (BTXA) into the puborectalis and/or external anal sphincter muscles. This is currently the second-line treatment for dyssynergic defaecation in whom biofeedback has failed. A systematic review in 2016 on the use of BTXA in patients with 'anismus', a term previously used to describe dyssynergic defaecation, demonstrated initial clinical improvement in symptoms in 77.4% of patients. Two of the seven studies were conducted on participants in whom biofeedback therapy had failed. Complications were reported in 7.4% of patients (0 to 22.6%) and included faecal incontinence, which was minor and transient, posterior anal fissure, and rectal prolapse. The effect of BTXA was not permanent, with clinical improvement declining to 46% at four months after the injection. For this reason, several studies offered repeated treatments.

The delivery of BTXA injection varied between studies and institutions in terms of dosage and position of injection, but all were performed via perianal or transanal approaches, often requiring sedation or anaesthesia. There are several disadvantages of this approach including cost (operating theatre utilisation) and risks associated with anaesthesia and infection from passing the needle through a contaminated operative field. In addition, the injection site is defined blind by the surgeon's finger (an issue of accuracy of injection and hazard of needle stick injury).

The proposed study aims to demonstrate the technical feasibility of an alternative approach to delivering BTXA injection in adult patients with dyssynergic defaecation. This novel technique injects BTXA into the puborectalis muscle percutaneously using an infracoccygeal approach under ultrasound guidance. This allows the procedure to be performed in an outpatient radiology setting without the need for any form of anaesthesia or analgesia. The injection

[figure not shown]

is performed in a clean operative field away from the anus, minimising risk of infection and the muscle can be clearly visualised (see below). These advantages will be particularly valuable in patients who require repeated procedures or those with multiple co-morbidities at high anaesthetic risk.

#### 5.2 Rationale

The utilisation of BTXA in human is well established. This medication is licensed for use in focal spasticity with well-established side-effects and interactions. Current evidence for the use of BTXA in dyssynergic defaecation is based on the conventional transanal approach, with report on efficacy and complications as previously stated.

Figure 1. Anatomy of the anal canal and rectum

[figure not shown]

[figure not shown]
*Rao et al, 2016*

The puborectalis (see Figure 1.) is easily accessible below the coccyx, and is the site for ultrasonic assessment in the paediatric population. The identification of puborectalis muscle in the infracoccygeal position has not been described in the literature in the adult population. However, pilot imaging studies on a small number of non-obese subjects have been successful in easily identifying the puborectalis using ultrasound scan (see Figure 2.). This approach has the potential to allow accurate administration of BTXA injection under ultrasonic guidance in the outpatient setting without the need for anaesthesia or operating theatre utilisation.

P = Puborectalis, Co = Coccyx, R = Rectum

(In prone position)

The general aim of this study is to demonstrate that percutaneous infracoccygeal BTXA injection is a valid alternative approach to transanal injection for the treatment of dyssynergic defaecation. Specifically, we will determine technical feasibility (including pilot proof of mechanism), patient acceptability, safety, and pilot efficacy outcomes for a future definitive trial.

#### 5.3 Risks / benefits

#### 5.3.1 Botulinum Toxin Type A related risks

The use of BTXA injection into the puborectalis and/or external anal sphincter muscles in patients with dyssynergic defaecation using the conventional transanal approach demonstrated initial clinical improvement in symptoms in 77.4% of patients, however in 46% of patients the effect was temporary and a repeat injection required.

The general side-effects of BTXA are stated in the British National Formulary. On review of current evidence (11 studies pertaining to 246 subjects), reported procedure specific side-effects relating to BTXA injection for the treatment of dyssynergic defaecation based on transanal injection include:

1. Temporary incontinence – faecal incontinence occurred in 17 cases (6.9%) from three studies and flatus incontinence

occurred in 10 cases (4.1%) from two studies. The symptoms were minor and temporary in all studies.

- Posterior anal fissure reported in two patients (0.8%) from a single study
- 3. Rectal prolapse reported in a single patient (0.4%) from a single study

#### 5.3.2 Risks related to injection

Risks associated with ultrasound scan can be categorised as diagnostic errors and biological effects. With regards to the risk of diagnostic errors, imaging the puborectalis using ultrasonography has been performed routinely as part of anorectal physiology studies but only using a transanal or perineal approach. The potential of diagnostic error (wrong muscle) using the percutaneous infracoccygeal approach is unknown but pilot imaging studies on a small number of healthy subjects demonstrate that it is easy to locate and obvious in terms of morphology. Further, volitional contraction can be used to demonstrate contraction under vision (see Figure 2).

Biological effects can be divided into thermal and mechanical effects. The National Council on Radiation Protection and Measurements (NCRP) report on the use of medical ultrasonography concluded that there is no evidence to suggest that ultrasound has caused any adverse effects, based on human epidemiological studies.

The BTXA injection will be delivered through a narrow-gauge needle as used daily for muscle injections by a variety of health professionals worldwide. Slight soreness can be associated with injection, but risks of infection and bleeding are rare (<1/10,000). We will record muscle activity (pilot proof of mechanism) using the same needle electrode avoiding further discomfort to the patient above that experienced from the injection alone.

Subcutaneous local anaesthetic infiltration with 1% lidocaine is routinely carried out for minor procedures. The general side-effects of lidocaine are stated in the British National Formulary. The maximum dosage is 4mg/kg (0.4ml/kg of 1% lidocaine) or 30ml, whichever is smaller. The amount required for this procedure is 5ml.

#### 5.3.3 Study benefits

Participants will add to the knowledge base for the treatment options for patients with dyssynergic defaecation. Though not certain, participants may also benefit from improvement in their constipation symptoms.

### 6. Study objectives

#### 6.1 Primary objective

The primary objective of this study is to establish the technical feasibility of percutaneous infracoccygeal BTXA injection to puborectalis muscle as an alternative to transanal puborectalis muscle injection for the treatment of dyssynergic defaecation.

#### 6.2 Secondary objective

- To assess safety of this technique
- To assess patient acceptability of this technique
- To derive pilot clinical efficacy data to inform future trials

#### 6.3 Primary endpoint

In order to measure technical practicability, the physician delivering the therapy will be asked to complete a physician acceptability questionnaire at the end of each procedure. The questionnaire subjectively measures the physician's opinion of the procedure difficulty, patient's discomfort, whether or not the procedure is considered successful, and any procedure limitations.

Question/Statement	Scoring
1. Patient's body habitus	kgcmBMI
2. Duration of procedure	minutes
3. Puborectalis identified by USS	□ At rest □ Voluntary contraction
4. Puborectalis identified by EMG	□ At rest □ Voluntary contraction
6. Difficulty of procedure	□ Easy □ Moderate □ Difficult
7. Reason for your answer in question 5.	(Free text)
8. Patient was comfortable	□ Strongly agree □ Agree □ Neutral □ Disagree □ Strongly disagree
9. Procedure was completed successfully	□ Strongly agree □ Agree □ Neutral □ Disagree □ Strongly disagree
10. Procedure limitations	(Free text)

Technical practicability will also be measured objectively by the rate of successful identification of the puborectalis:

- Using ultrasound scan at rest and under voluntary contraction
- Using EMG at rest and under voluntary contraction

#### 6.4 Secondary endpoint

#### 6.4.1 Safety

Expected adverse event (AE) related to BTXA injection of the puborectalis include:

- Bruising at injection site
- Local skin reaction at injection site
- Pain at injection site
- Infection at injection site
- New or worsening faecal incontinence

Following the injection, any adverse event reported by the patients will be recorded on the adverse event (AE) form on the patient's eCRF using Research Electronic Data Capture (REDCap). This form will record the nature, severity, time of onset of, and treatment required for the AE. Patients are encouraged to self-report any adverse events as soon as possible by telephone. If no adverse events have been self-reported this will be confirmed with the patient at the end of every follow-up appointment as part of the follow-up procedure. In addition, at the time of first follow-up the injection site will be inspected for any signs of bruising, local skin reaction, or infection. At each follow-up, St. Mark's incontinence score will also be measured to allow detection of new or worsening incontinence, which is the main procedure specific risk associated with this procedure.

The severity of any adverse events will be classified according to the Clavien-Dindo classification of surgical complications:

- Grade 1 any deviation from normal post-operative course without need for pharmacological (antiemetics, antipyretics, analgesics, diuretics, and electrolytes are permitted), surgical, endoscopy, or radiological interventions
- Grade 2 requiring pharmacological treatment other than those permitted in 1 (including blood transfusion and total parenteral nutrition)
- Grade 3 requiring surgical, endoscopic, or radiological intervention
  - Grade 3a not under general anaesthetic
  - Grade 3b under general anaesthetic
- Grade 4 life-threatening complication requiring intensive care management
  - Grade 4a single organ dysfunction, including dialysis
  - Grade 4b multi-organ dysfunction
- Grade 5 death

Serious adverse events (SAE) will be recorded as above and will also be reported as described in the safety reporting section (see Section 16).

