### 8. Study design

The overall design is of a single-centre, prospective, uncontrolled, open-label observational study. Patients diagnosed with dyssynergic defaecation, using Rome IV criteria, will be identified from weekly pelvic floor MDT and current waiting list for biofeedback therapy and invited to participate. BTXA injection is not offered as an alternative to biofeedback and does not preclude patients from receiving biofeedback therapy as per standard treatment as this is not a study of treatment efficacy.

All participants will undergo BTXA injection within 12 weeks of recruitment.

Data collection:

- Baseline data collection from patient's initial symptoms questionnaire and anorectal physiology report (pre-procedure).
- MYMOP questionnaire (pre-procedure and at final follow-up)
- Patient and physician procedural questionnaire to be completed at the end of the BTXA injection procedure (see Section 5.3 and 5.4).
- Cleveland clinic constipation score and St. Mark's incontinence score to be completed by the patient at each follow-up.
- Anorectal physiology report (post-procedure) for anorectal manometry results at first follow-up.
- Any adverse events reported by the patient will be recorded on an adverse event form (see Section 5.4).

Data analysis:

- Feasibility and efficacy outcomes will be extracted from the questionnaires and reports and recorded onto Research Electronic Data Capture (REDCap).
- Anonymised summary data will be exported to Excel and descriptive statistics (e.g. mean, confidence intervals of effect) used to present data for publication.

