#### Visit 3: BTXA injection

The BTXA injection will be scheduled by the radiology department within 12 weeks. The patient and radiologist carrying out the injection will complete a procedurerelated questionnaire after the procedure. Ultrasound and EMG report on each patient will be obtained following the procedure. The patient will be asked to report any adverse events following the BTXA injection as soon as possible by phone or at follow-up.

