At any stage of the study, expected adverse events will be recorded on the patient's eCRF. If no adverse events have been self-reported this will be confirmed with the patient at the end of every follow-up appointment as part of the follow-up procedure. Serious or unexpected adverse events will be recorded and also reported according to research governance framework guidelines (see Section 14).

Patients can withdraw at any point in the study without the requirement to provide a reason. The data collected from the point of consent to the point of withdrawal will be kept for analysis of retention and follow-up rate, as well as incidents of adverse events depending on the stage at withdrawal. Such patients will return to routine care.

					-~~{	Lon				

Figure 3a. EMG of puborectalis demonstrating tonic activity at rest

Figure 3b. EMG of puborectalis demonstrating voluntary contraction

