### 16. Safety reporting

All adverse events (AE) related to or thought to be related to the procedure will be recorded in the patient's eCRF using an adverse event form. This form will record the nature, severity, time of onset of, and treatment required for the AE. Severity of the AE is graded according to the Clavien-Dindo classification (see Section 5.4)

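### Sections 6.4.1, 8 and 9 word adverse event capture as patient report after the injection, which is narrower than Section 16 on who reports, and neither procedure-day form asks the operator whether an event occurred

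*Combined protocol and SAP*

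**What the plan says.** Three places describe capture through the patient.

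- Section 6.4.1: "Following the injection, any adverse event reported by the patients will be recorded on the adverse event (AE) form".
- Section 8, data collection list: "Any adverse events reported by the patient will be recorded on an adverse event form".
- Section 9, visit 3: "The patient will be asked to report any adverse events following the BTXA injection as soon as possible by phone or at follow-up".

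Two places are wider.

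- Section 16, opening paragraph: "All adverse events (AE) related to or thought to be related to the procedure will be recorded in the patient's eCRF".
- Section 9, text after the visit descriptions: "At any stage of the study, expected adverse events will be recorded on the patient's eCRF". The same paragraph says that serious or unexpected events are recorded as well.

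Section 6.4.1 is not purely patient-reported. It adds that "at the time of first follow-up the injection site will be inspected for any signs of bruising, local skin reaction, or infection", and it has the St. Mark's incontinence score measured at each follow-up. Both come after the procedure day.

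Two forms are completed at visit 3. The physician form in Section 6.3 covers body habitus, duration, identification of the muscle by ultrasound and EMG, difficulty, patient comfort, successful completion and free text on "procedure limitations". The patient form in Section 6.4.2 covers pain, embarrassment, comfort, duration, overall acceptability and willingness to repeat.

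**The concern.** The operator is the main observer of what happens while the needle is in. Section 9 places the patient prone, so the patient sees neither the needle nor the ultrasound image. A radiologist carries out visit 3, and the clinical or research team carries out the follow-up visits. The first scheduled enquiry and site inspection come at 4-6 weeks, when a brief procedural event may have left no trace.

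Section 5.1 presents the technique as novel, and Section 5.3.2 says the potential for targeting the wrong muscle by this route is unknown. Assessing safety is the first secondary objective in Section 6.2. If the one person placed to see a procedural event is never asked, capture rests on that person volunteering it. The report could then state that no procedural events occurred without a recorded negative answer behind the statement.

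**Working it through.** The plan gives no figure to reproduce: Section 11.1 calls the 10 patients a convenience sample, and no event rate is assumed. The check is mainly a comparison of text.

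**Step 1: who may report, and when.**

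| Place | Source of the event | Timing |
|---|---|---|
| 6.4.1, recording sentence | Patient | After injection |
| 6.4.1, site inspection and incontinence score | Staff inspection; patient-completed score | Follow-up visits |
| 8, data collection | Patient | Not stated |
| 9, visit 3 | Patient | After injection, by phone or at follow-up |
| 9, closing text | Not restricted | Any stage |
| 16, opening paragraph | Not restricted, if related or thought to be related to the procedure | Not restricted |
| 16.2 | Foresees a reporting investigator | Not restricted |

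The first group is narrower than the last three rows on who reports. (Section 16 is narrower in another respect, since its opening paragraph covers only events thought related.) Section 16.1 defines an adverse event for a participant who has been given an intervention. That leaves some doubt about events at local anaesthetic or needle insertion, before the toxin is given, but the reference to the procedure in the opening paragraph of Section 16 would cover them.

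**Step 2: is the operator asked?** No listed item on the physician form asks about an event or complication, and neither does the prose description of the form. The nearest items are successful completion and the free-text limitations field. The patient form has no such item either.

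**Step 3: what one missed event does with n = 10.** Exact (Clopper-Pearson) two-sided 95% limits:

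- 1/10, lower limit: 1 − 0.975^(1/10) = 0.0025, or 0.3%.
- 1/10, upper limit: the p that solves (1 − p)^10 + 10p(1 − p)^9 = 0.025, giving p = 0.445, or 44.5%.
- 0/10, lower limit: 0%.
- 0/10, upper limit: 1 − 0.025^(1/10) = 0.308, or 30.8%.

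The observed rate falls by 10 percentage points, and the upper limit by 44.5 − 30.8 = 13.7 points.

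**Step 4: how likely is there to be an event to miss?** The documents give no rate for events during this procedure, so the rates below are assumptions. The chance of at least one event in 10 procedures is 1 − (1 − p)^10:

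| Assumed rate p | Chance of at least one event |
|---|---|
| 1% | 9.6% |
| 5% | 40.1% |
| 10% | 65.1% |
| 20% | 89.3% |

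**The case against.** The strongest reply is that the plan already provides for these events. Section 16 sends every procedure-related event to the eCRF, whoever saw it. Section 9 covers any stage, and Section 16.3 names the source documents, the CRF and, where appropriate, the medical records. The label in the visit table of Section 9, broken in the extracted text, appears to read as adverse events reporting and to begin at visit 3. The operator can also record a stopped procedure through the completion item and the limitations field, and the radiology report is transferred to the eCRF. All of this stands. A reader of 6.4.1 alone might infer that operator-observed events have no collection route at all, and the documents do not support that.

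Two further inferences should also be resisted.

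- Section 5.1 counts against the transanal route "an issue of accuracy of injection and hazard of needle stick injury", so a reader might think the study must measure needle-stick. But an operator injury is not an event in a participant under Section 16.1, and it is not an endpoint in Section 6. Recording it is optional.
- A reader might expect the clean-field argument to depend on what the operator sees. Section 5.1 ties that argument to infection, which appears later and is covered by patient report and site inspection.

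It is also fair to say that the patient would usually know of a faint or visible bleeding, that Section 11.2 plans only a qualitative summary of reported events, and that the intervals above would apply to any single missed event in any 10-patient study. In the available text the physician form's numbering runs from 4 to 6, so a lost row cannot be ruled out, although the prose description mentions no complication item.

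None of this supplies the prompt. A place to record an event does not ensure that anyone is asked about it.

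**Conclusion.** The concern holds as a gap in prompting and an inconsistency in wording, not as a missing route. On who may report, the capture rule in Sections 6.4.1, 8 and 9 (visit 3) is narrower than Section 16 and the closing text of Section 9. No procedure-day item asks the operator for a yes or a no. A finding of no procedural events would therefore be ambiguous.

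The size is one event in ten: 10% (0.3% to 44.5%) against 0% (0% to 30.8%). This shows the effect of a single omission; it does not predict that one will occur. It assumes that the physician form is as shown in Section 6.3 and that an event seen only by the operator could go unvolunteered. The point does not threaten the primary endpoint, but it bears directly on a stated secondary objective and is worth correcting because the correction is so small.

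**What to change.** 1. Add one item to the physician form in Section 6.3: *Any adverse event or complication during the procedure: none / yes (specify, e.g. needle entered anal canal or rectum, bleeding, faint, other)*. Any *yes* opens the adverse event form.
2. In Sections 6.4.1 and 8, change the source of events to *reported by the patient or observed by the operator or study team*, so that they agree with Section 16 on who may report. The visit 3 text can then stand as the instruction to the patient.
3. Optional: a separate staff-event tick for operator needle-stick, and an adverse event row in the source data table in Section 14.2. The second is clerical.

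The cost is one item on a form already completed after each procedure and two wording changes. No visit, staff time beyond the tick, or sample size changes.

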#### Visit 4: first follow-up

The patient will attend first follow-up 4-6 weeks after the injection and complete the Cleveland Clinic constipation scoring (CCCS) as well as St. Mark's incontinence scoring (SMIS). They also undergo a repeat anorectal physiology tests.

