#### **15.3Medicinal product**

Botulinum toxin type A (Botox, Allergan, Ireland)

- Indication: focal muscular spasm (of the puborectalis in dyssynergic defaecation)
- Licensing status: PL 00426/0119
- Dosing schedule: injection of 200 units once
- Route of administration: intramuscular injection (to puborectalis muscle)
- Source of Medicinal Product: Royal London Hospital pharmacy
- Storage and dispensing: product will be dispensed on the day of the procedure and stored in a refrigerator before use
- Contraindications:
  - o Known hypersensitivity to BTXA, human albumin, sodium chloride
  - Presence of infection at the proposed injection site
- Side-effects:
  - Common or very common: alopecia; asthenia; autonomic dysreflexia; bladder diverticulum; constipation; dizziness; drowsiness; dry eye; dry mouth; dysphagia (most common after injection into sternocleidomastoid muscle and salivary gland); ecchymosis (minimised by applying gentle pressure at injection site immediately after injection); eye discomfort; eye disorders; eye inflammation; fall; fever; gait abnormal; haematuria; headaches; hot flush; increased risk of infection; influenza like illness; insomnia; joint disorders; leukocyturia; malaise; muscle complaints; muscle weakness; musculoskeletal stiffness; nausea; neuromuscular dysfunction; oedema; pain; paresis; sensation abnormal; skin reactions; subcutaneous nodule; urinary disorders; vision disorders
  - Uncommon: anxiety; coordination abnormal; depression; dysphonia; dyspnoea; facial paralysis; memory loss; oral paraesthesia; photosensitivity reaction; postural hypotension; speech impairment; taste altered; vertigo
  - Frequency not known: abdominal pain; angioedema; angle closure glaucoma; appetite decreased; arrhythmia; diarrhoea; hearing impairment; hypersensitivity; myocardial infarction;

myopathy; nerve disorders; respiratory disorders; seizure; syncope; tinnitus; vomiting

- Procedure specific:
  - Temporary incontinence faecal incontinence occurred in 17 cases (6.9%) from three studies and flatus incontinence occurred in 10 cases (4.1%) from two studies. The symptoms were minor and temporary in all studies.
  - Posterior anal fissure reported in two patients (0.8%) from a single study
  - Rectal prolapse reported in a single patient (0.4%) from a single study

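### Posterior anal fissure and rectal prolapse are named as procedure-specific risks, but no question, form item or examination in the safety plan is aimed at them

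*Combined protocol and SAP*

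**What the plan says.** **Named risks.** Section 5.3.1 introduces its list with "On review of current evidence (11 studies pertaining to 246 subjects), reported procedure specific side-effects" and bases it on transanal injection. The list includes "Rectal prolapse reported in a single patient (0.4%) from a single study". Section 15.3 repeats the list, including "Posterior anal fissure reported in two patients (0.8%) from a single study". Both events carry the same citation. Section 5.1 also mentions both as complications.

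**Expected events.** Section 6.4.1 begins "Expected adverse event (AE) related to BTXA injection of the puborectalis include" and gives four injection-site items (bruising, skin reaction, pain, infection) and faecal incontinence. Fissure and prolapse are not among them.

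**How events are found.**
- The stated inspection is of the injection site, once: "at the time of first follow-up the injection site will be inspected for any signs of bruising, local skin reaction, or infection".
- The St. Mark's incontinence score is taken at baseline (visit 2) and at each follow-up.
- Under 6.4.1, whatever the patient reports is recorded. Patients are encouraged to telephone, and if nothing has been reported this is confirmed at each follow-up.
- At visit 4, "They also undergo a repeat anorectal physiology tests". Section 6.4.3 describes these as manometry to judge the need for further treatment.
- Visits 5 and 6 may be held by telephone or online.

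**Recording and reporting.** The opening of section 16 speaks of recording events that are, or are thought to be, related to the procedure. Section 16.4 treats an event as unexpected if the protocol or other reference safety information does not list it as expected.

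**The concern.** Safety is the first secondary objective, and section 5.2 presents the new route as a valid alternative to the transanal one. Readers will set the results beside the transanal complications in 5.3.1. For two of those complications the plan has no targeted means of detection.

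Section 7.1 selects patients on features such as straining, a sense of blockage and incomplete evacuation. Such a patient could plausibly take anal pain, bleeding or a lump as part of the existing complaint and not offer it as an adverse event. That is a judgement about reporting behaviour; the documents give no data on it. If the symptom is mentioned but attributed to constipation, 6.4.1 would record it, whereas the opening of section 16 does not clearly commit to doing so.

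Two things are at stake: an affected patient may go unrecognised, and the expectedness of a serious fissure or prolapse under 16.4 would be open to argument.

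**Working it through.** **1. The plan's own rates** (5.3.1 and 15.3, denominator 246)
- Faecal incontinence: 17/246 = 6.9%
- Flatus incontinence: 10/246 = 4.1%
- Posterior anal fissure: 2/246 = 0.8%
- Rectal prolapse: 1/246 = 0.4%

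All four agree with the stated percentages.

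**2. Events with no targeted ascertainment**
- Fissure plus prolapse: 2 + 1 = 3, and 3/246 = 1.2%, assuming that no patient had both.
- All listed procedure-specific events: 17 + 10 + 2 + 1 = 30. The share without targeted ascertainment is 3/30 = 10%.

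**3. What 10 patients could show.** This carries the transanal rates over to the infracoccygeal route, which is an assumption.
- Expected cases of fissure or prolapse: 10 × 3/246 = 0.12.
- Chance of at least one case with perfect detection, 1 − (1 − p)^10: fissure 7.8%, prolapse 4.0%, either 11.5%.
- Zero fissures would therefore be seen about 92% of the time, and zero prolapses about 96%, even if every case were found.

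**4. Exact 95% upper limit when 0 of 10 are observed**
- One-sided: 1 − 0.05^(1/10) = 25.9%
- Two-sided: 1 − 0.025^(1/10) = 30.8%

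**5. Effect of imperfect detection.** Let s be the probability that a true case is recorded. The documents give no value, so a range is shown. The upper limit becomes the limit in step 4 divided by s, and the chance of recording at least one case becomes 1 − (1 − s·p)^10.

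| s (assumed) | Upper limit, one-sided | Upper limit, two-sided | Chance of recording ≥1 fissure | Chance of recording ≥1 prolapse |
|---|---|---|---|---|
| 1.00 | 25.9% | 30.8% | 7.8% | 4.0% |
| 0.75 | 34.5% | 41.1% | 5.9% | 3.0% |
| 0.50 | 51.8% | 61.7% | 4.0% | 2.0% |
| 0.25 | 100% (capped) | 100% (capped) | 2.0% | 1.0% |

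Weak ascertainment widens an interval that is already very wide.

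**6. The sections side by side.** Fissure and prolapse appear in 5.3.1 and 15.3 as side-effects but not in 6.4.1 as expected. Section 16.4 turns on whether an event is listed as expected, so the two sets of text lead to different answers. On recording, 6.4.1 covers any event the patient reports, and 16.1 defines adverse events irrespective of cause; the opening of section 16 is narrower.

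**The case against.** The strongest reply is that the expected-event list is not a detection checklist. Its wording leaves it open-ended, unlisted events are still recorded under 6.4.1, adverse-event status is checked at every follow-up, and section 9 requires unexpected events to be recorded and reported. The study is a descriptive convenience sample of 10 with no hypothesis tests, and it plans no formal comparison with transanal rates. The fissure and prolapse rates come from a different route and one cited study.

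Much of this stands. Omission from the list does not itself prevent recording, and the expected number of cases is tiny. What remains is that the general check depends on the patient recognising the symptom as an adverse event, and that the sections disagree on what is recorded and what counts as expected.

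Two stronger readings are tempting, and the documents support neither.

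- **Flatus incontinence is also unmonitored.** Section 5.3.1 names it and the expected list does not. Adding its 10 cases would give 13/30 = 43% of listed events without a place in the monitoring. But 6.4.1 uses the St. Mark's score to detect the onset or worsening of incontinence in general. The score's items are not reproduced, so whether it picks out flatus can be neither confirmed nor denied. Only the 3/30 is supportable.
- **Looking for these events would make a nil result meaningful.** Step 4 shows otherwise: with perfect detection the upper limit is still 26% to 31%, against rates of 0.8% and 0.4%. The sample size is the main limit, and no inspection removes it.

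**Conclusion.** The point holds as a gap in ascertainment and a disagreement between sections, confined to fissure and prolapse. Two risks that the protocol itself names, at 3 of 246 subjects (1.2%) and 10% of its listed procedure-specific events, have no question, form item or examination directed at them. Their recording and expectedness also differ by section. It is a minor point: about 0.12 cases would be expected in 10 patients, safety is a secondary objective, and the primary feasibility result is untouched.

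This rests on two assumptions: that the transanal rates are a usable guide for the new route, and that some patients would attribute anal symptoms to their constipation. The mismatch between sections depends on neither.

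**What to change.** - **Adverse-event form, visits 4 to 6, including telephone and online versions:** add short items on anal pain or bleeding, and on prolapse or a lump. Ask the same items once at visit 2 as baseline.
- **Visit 4 form:** record whether fissure or external prolapse was seen at the physiology appointment already scheduled, with an option for not looked for. External prolapse is excluded at entry (7.2), so a new one would be interpretable.
- **Recording:** reconcile the opening of section 16 with 6.4.1 so that these events are recorded whatever their presumed cause.
- **Expectedness:** reconcile 5.3.1 and 15.3 with the list in 6.4.1 so that the status of each named event under 16.4 is unambiguous.
- **Reporting (11.2):** give each count out of 10 with an exact interval. State that 0/10 leaves a 95% upper limit of about 26% (one-sided) or 31% (two-sided) and so cannot support a comparison with transanal rates.

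The cost is a few form items and some wording changes, with no new visit and no change in sample size. Prompting will pick up some minor or pre-existing symptoms; the visit 2 baseline allows these to be separated from new ones.
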